### 71. Section 9.4.1. – Analysis Populations

**All Evaluable Subjects Population:** This is the population used for decision-making at the futility analysis during part 2 (Expansion Cohort). This will be the population for Bayesian predictive adaptive design as defined in Section 9.5.2 and summaries of response if data warrant. In general, subjects are evaluable if they have received at least 1 dose of treatment for both drugs and the time from the first dose to the time of data cut-off is more than 66 days, i.e., reached the time of three planned disease assessments. Details on deriving the evaluable population will be provided in the RAP. Subjects are considered evaluable if they are in the all treated population, have received at least 2 doses of treatment, and have had at least one disease assessment post 2nd dose. Subjects

~~are also considered evaluable if they are in the all treated population and have progressed or died or have permanently discontinued from the study treatment~~

**Reason for change:** Revised definition to allow flexibility based on possible delays with dosing based on FTIH experience.

## 72. Section 9.5 – Interim Analysis

### Section 9.5.1. – Part 1: Dose Escalation

During dose escalation, no formal interim analysis will be performed. Data will be reviewed through data visualization tool to inform dose escalation decisions. The mTPI design will be utilized to guide dose escalation/de-escalation decisions. More details of the dose escalation procedure are described in Section 4.2.3.1.

After the last cohort of subjects in Part 1 complete the DLT observation period, a formal interim analysis will be performed to support the RP2D decision, except for scenarios where RP2D is clearly defined by the toxicity profile. Data considered to support RP2D decision will include but not limited to safety, available PK profile and observed signs of clinical activity. Details of the interim analysis will be provided in the RAP.

~~While no formal interim analysis is planned for Part 1, safety data will be examined on an ongoing basis to support dose escalation decisions. Prior to determining the GSK2857916 dose in combination with 200 mg pembrolizumab for the next cohort, analysis of safety data from previous dose cohort will be performed. The analysis will be performed after at least 3 evaluable subjects have been studied per dose level. To facilitate dose escalation/de-escalation decisions, a Bayesian logistic regression model (BLRM) may be utilized to predict the probability of DLT at the dose levels to be tested. Specifically, a BLM for combination treatment will be fitted on the dose limiting toxicity data (i.e., absence or presence of DLT) accumulated throughout the dose escalation to model the dose toxicity relationship of GSK2857916 in combination with pembrolizumab. The BLM analysis will be performed to determine if a next dose level is expected to be safe and to support the dose escalation decision following the completion of each dose cohort. Further details regarding such analyses including prior specifications will be provided in the Reporting and Analysis Plan (RAP).~~

### Section 9.5.2. – Part 2: Expansion

Continuous safety monitoring will be conducted for the expansion cohort starting from when 5 subjects are dosed. The observed number of treatment-related Grade 4 or higher AEs will be compared against the safety stopping rule in Table 12. Enrollment may stop if the safety stopping rule is met based on totality of safety data. For example, if there are 3 events out of 5 dosed subjects, enrollment may stop after review of all safety data, if there are 2 or fewer events out of 5 dosed subjects, enrollment will continue. Operating characteristics for the safety stopping rule are provided in Appendix 11.

**Table 12 Safety Stopping Rules for the Expansion Cohort**

Number of dosed subjects		Stop if treatment related Grade 4 or higher AEs larger or equal to this number
5		3
6-10		4
11-14		5
15-19		6
20-25		7
26-28		8

~~A Bayesian predictive adaptive design [Lee, 2008] as described in Section 9.2.2 that allows the trial to be monitored more frequently at multiple stages will be used.~~

~~For the expansion cohort, based on the size of expansion cohort and on anticipated enrollment pace, it is considered that a single futility analysis is practical and sufficient once approximately 15 subjects in Part 2 are evaluable for futility analysis. The number of best unconfirmed overall responses (PR+VGPR+CR+sCR) observed for the All Evaluable Subjects Population will be compared with the stopping rules provided in Table 13. Additional futility looks maybe performed, if necessary. These rules are intended as a guideline only. Actual decisions will depend on the totality of the data, in particular, the depth and duration of response will also be taken into account before declaring futility. Should the recommendation to stop for futility be disregarded in favor of a decision to continue the trial based on the totality of the data, the overall type I error rate of the expansion phase will be inflated. When the total sample size reaches 30 and 16 responders are observed, with the assumed beta prior distribution as described in Section 9.2.2., the posterior probability of ORR>40% is 92.9%.~~

Interim analyses for ORR will start when at least 10 subjects are evaluable as defined in Section 9.4.1. Subjects who initially received RP2D in Part 1 may also be included. The observed number of subjects with unconfirmed response of PR or better will be compared with the stopping boundary in Table 13. Enrolment may stop if the stopping rule is met. Final decision will be based on the totality of data. For example, if there are 2 unconfirmed responses out of 10 evaluable subjects, enrolment may stop after review of all available data; if there are 3 or more unconfirmed responses out of 10 evaluable subjects, enrolment will continue.

Table 12 updated to Table 13 due to inclusion of Table 12. Table 13 was updated with revised numbers for Decision Making Criteria for Futility Analysis based on the updated subject total.

**Reason for change:** Replaced BLRM with mTPI model for Dose Escalation part. Added safety monitoring criteria based on rate of Grade 4 treatment related AEs due to FDA request to add stopping criteria. Updated Part 2 Table 13 futility wording due to change in subject number.

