During part 2 of the study, treatment-rated Grade 4 or higher AEs will be continuously monitored starting from when 5 subjects are dosed. If observed toxicity level is significantly higher than 12% at 1-sided alpha of 0.025, the study may be terminated early based on totality of safety data. The 12% threshold is chosen based on 11% Grade 4 or higher AE observed in study BMA117159.

For Part 2, futility analyses for ORR will start when 10 subjects are evaluable. Enrollment may stop if the stopping rule is met based on totality of data.

~~Final analysis of the data captured in Part 1 and Part 2 will be undertaken after all subjects meet at least one of the following criteria: have reached the end of study or died. End of study is defined as when all subjects have been followed for 36 months from first dose of study treatment or died or withdrew consent or are lost to follow-up or the safety stopping criteria is met, whichever occurs first. have received all prespecified treatments (32 cycles) or have progressed; or has died; or has been permanently withdrawn from the study for toxicity or other reasons.~~

**Reason for change:** Revisions to statistical calculations and wording based on change to subject number, switch to mTPI design and clarification of end of study definition.

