## 69. Section 9.1.2. – Part 2: Expansion cohort

The primary goal of Part 2 is to characterize clinical activity of the combination and to detect if meaningful response rate (ORR) can be achieved. Based on historical information [Lokhorst, 2015] and clinical judgement, the null hypothesis has been defined as ORR  $\leq 40\%$  ~~for the purpose of this study~~. The alternative hypothesis has been defined as ORR  $\geq 60\%$  ~~based on clinically meaningful improvement of 20%. A test will be performed using the stopping rules provided in Section 9.5.2. Descriptive statistics will be used to describe the observed ORRs in the expanded cohorts.~~

In Part 2, treatment-related Grade 4 or higher AEs will be continuously monitored starting from when 5 participants are dosed. Based on the 11% Grade 4 or higher AEs observed in the FTIH study (BMA117159), it is considered that the combination treatment has unacceptable toxicity if observed treatment-related Grade 4 or higher AEs is significantly higher than 12% at 1-sided alpha of 0.025.

**Reason for change:** Clarified that the increase of alternative hypothesis relates to clinical improvement and addition of FDA requested stopping criteria for Part 2.

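### The Part 2 safety stopping rule counts treatment-related Grade 4 or higher AEs, but its boundaries are exact binomial limits for subjects, so one subject with several AEs can meet it

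*Protocol*

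**What the plan says.** The criterion is set in Section 9.1.2: toxicity is unacceptable "if observed treatment-related Grade 4 or higher AEs is significantly higher than 12% at 1-sided alpha of 0.025". The synopsis gives the same limit, "If observed toxicity level is significantly higher than 12% at 1-sided alpha of 0.025", and its source: "The 12% threshold is chosen based on 11% Grade 4 or higher AE observed in study BMA117159".

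Section 9.5.2 puts the criterion into operation from the fifth dosed subject onward: "The observed number of treatment-related Grade 4 or higher AEs will be compared against the safety stopping rule in Table 12". The table's row index is "Number of dosed subjects" and its boundary column is headed "Stop if treatment related Grade 4 or higher AEs larger or equal to this number". The boundaries are 3 at 5 subjects, 4 at 6–10, 5 at 11–14, 6 at 15–19, 7 at 20–25 and 8 at 26–28. The worked example reads "if there are 3 events out of 5 dosed subjects, enrollment may stop after review of all safety data".

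Nothing in the text at hand says that a subject with several such AEs counts once. The response futility rule in the same section does name subjects as its counting unit.

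**The concern.** The numerator is a number of AEs and the denominator a number of subjects. A test against 12% needs a numerator in which each subject contributes 0 or 1. If one subject can contribute two or three, the count is no longer binomial and can even exceed the number dosed.

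This is the Part 2 stopping rule added at the FDA's request. With the present wording, two people holding the same data could disagree on whether it has been met. On the literal reading, a combination with an acceptable subject-level rate would reach the boundary more often than the limits were built to allow.

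**Working it through.** **Inputs from the protocol.** Reference rate p0 = 0.12 and one-sided 0.025 (Section 9.1.2, synopsis); looks at every n from 5 to 28 and the boundaries b(n) (Section 9.5.2 and its table). **Input not in the protocol.** The mean number m of treatment-related Grade 4 or higher AEs per affected subject; a range of 1.0 to 2.0 is assumed.

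**Step 1: reproduce the table.** Take b(n) as the smallest k with P(X ≥ k) ≤ 0.025, where X ~ Binomial(n, 0.12) and X counts subjects. For n = 5, k = 3:

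10 × 0.12³ × 0.88² + 5 × 0.12⁴ × 0.88 + 0.12⁵ = 0.01338 + 0.00091 + 0.00002 = 0.0143.

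At k = 2 the tail is 0.1125, so the boundary is 3, as printed. For all rows:

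| Dosed subjects | Printed boundary | Tail at boundary, range over the row | Smallest tail one below the boundary |
|---|---|---|---|
| 5 | 3 | 1.43% | 11.25% |
| 6–10 | 4 | 0.25% to 2.39% | 2.61% |
| 11–14 | 5 | 0.61% to 1.96% | 3.41% |
| 15–19 | 6 | 0.57% to 2.02% | 2.65% |
| 20–25 | 7 | 0.67% to 2.43% | 2.60% |
| 26–28 | 8 | 0.91% to 1.45% | 2.99% |

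All 24 values of n match. Other constructions do not: p0 = 0.11 matches 17 of 24, p0 = 0.13 matches 19, and a score test (z > 1.96) gives lower boundaries at many n, for example 3 at n = 6. The table is therefore an exact limit for a count of subjects.

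**Step 2: chance of ever crossing, counting subjects.** An exact recursion carries the distribution of the count from n = 1 to 28 and removes, at each n ≥ 5, the paths that have reached b(n). At a true 12% it gives 5.6%.

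**Step 3: count AEs as the text says.** Each subject contributes 0 with probability 0.88, and otherwise 1 + Poisson(m − 1) AEs. The subject-level rate stays at 12%. The same recursion, and the single-look tail at selected n, give:

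| m | n=5 | n=10 | n=14 | n=19 | n=25 | n=28 | Ever crossing |
|---|---|---|---|---|---|---|---|
| 1.0 | 1.4% | 2.4% | 2.0% | 2.0% | 2.4% | 1.5% | 5.6% |
| 1.1 | 3.4% | 5.0% | 4.5% | 4.7% | 5.6% | 3.9% | 11.5% |
| 1.25 | 6.3% | 9.1% | 8.7% | 9.5% | 11.3% | 8.9% | 20.5% |
| 1.5 | 10.9% | 15.7% | 16.1% | 18.2% | 21.6% | 18.8% | 34.2% |
| 2.0 | 19.4% | 27.3% | 29.7% | 34.1% | 40.2% | 38.1% | 55.1% |

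**Step 4: the simplest case.** One subject with three such AEs among the first five meets the boundary of 3, although 1 of 5 subjects is affected. A single subject reaching the boundary alone is realistic mainly at early looks (3 AEs at n = 5, 4 at n = 6–10). Later, the inflation comes from several subjects with repeat events.

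**The case against.** The strongest reply is that subjects were always meant. The boundaries reproduce only that way, the example sets events against dosed subjects, and the protocol reports AE percentages by subject elsewhere. That stands, and it is why the repair is wording and not a new design. It does not remove the defect, because the rule as written still instructs the reader to count AEs.

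The second reply is that the consequence is limited. Meeting the boundary leads to a review of all safety data, after which enrolment may stop; an internal safety review committee outside the study team also reviews safety data. That stands too. One subject's cluster of events would be visible at review, and the error runs towards more scrutiny.

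Two stronger readings are tempting and are not supported.

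- A reader might infer that an overall 2.5% error is promised and lost, since repeated looks give 5.6%. The text at hand claims no overall 2.5%. The 0.025 describes when an observed rate is significantly high, and counted by subject it holds at every look. Operating characteristics are assigned to Appendix 11, whose figure is not shown, so the cumulative figure may already be there.
- A reader might infer that the 11% reference is defined differently from the monitored events, because *related* is missing where it is cited. That may be shorthand, and the protocol does not settle it.

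Finally, the wording comes from the Amendment 1 summary of changes, as the new text. The Amendment 2 and 3 change lists shown report no revision of this rule, but Amendment 2 gives the number Table 12 to a pharmacokinetic sampling table. The current section and table number need checking.

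**Conclusion.** The point holds as a mismatch of counting unit in a decision rule. The text counts AEs and the boundaries are valid for subjects. That much rests on exact arithmetic, with 24 of 24 boundaries reproduced.

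The size of the effect is conditional. Taking a true 12% subject rate and the assumed 1 + Poisson pattern, the chance of ever crossing rises from 5.6% to between 11.5% (mean 1.1 AEs per affected subject) and 55% (mean 2.0). If every affected subject had exactly one event, nothing would change. The practical consequence is an unwarranted review and a possible enrolment stop, not an automatic one, and the test of the primary endpoint is not affected.

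**What to change.** In the safety stopping table (Table 12 in Amendment 1, possibly renumbered since), Sections 9.5.2 and 9.1.2 and the synopsis, replace the AE count with: *number of subjects with at least one treatment-related Grade 4 or higher AE, each subject counted once*. Reword the worked example to say 3 affected subjects out of 5 dosed. Add one sentence stating that 0.025 is the per-look level and that the chance of ever crossing at a true 12% is about 5.6%, and check that Appendix 11 agrees.

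The boundaries stay as they are. The cost is a wording change in an amendment, with matching wording in the safety review committee's charter where it repeats the rule. There is no change to sample size, look schedule or data collection.

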### 73. Section 9.6 – Final Analysis

Final analysis of the data captured in Part 1 and Part 2 will be undertaken at the end of the study (Section 5.5.2), ~~after all subjects meet at least one of the following criteria: have received all prespecified treatment (32 cycles) or has progressed; or has died; or has been permanently withdrawn from the study~~. Data from the two parts may be combined for some analyses at the end of the trial, as appropriate.

**Reason for change:** Revised criteria for end of study analysis.

### 74. Section 9.7.1. – Clinical Activity Analyses

The primary endpoint ORR and other applicable secondary endpoints (e.g., CBR, DoR, TTR, TTP, PFS) will be based on the responses assessed by the investigator.

At futility interim, the primary endpoint (ORR) will be analyzed based on the All Evaluable population. Otherwise, all efficacy endpoints will be analyzed based on the All Treated population unless otherwise specified.

The analytical methods planned for each endpoint are described in Table 14.

**Table 14      Statistical Analysis Methods for Clinical Activity Endpoints (Part 2)**

Endpoint	Statistical Analysis Methods
Primary	
Overall Response Rate (ORR) is defined as the percentage of subjects with a confirmed PR or better (i.e. PR, VGPR, CR and sCR), according to the International Myeloma Working Group (IMWG) Response Criteria.
 
The number and percentage of subjects in the following response categories will be presented: sCR, CR, VGPR, PR, overall response (sCR+CR+VGPR+PR), minimal response (MR), stable disease (SD), progressive disease (PD), and not evaluable (NE). The corresponding 95% CI for ORR will also be provided. Subjects with unknown or missing responses will be treated as non-responders, i.e., these subjects will be included in the denominator when calculating percentages of response.

Secondary	
Secondary clinical activity endpoints of Part 2 of this study are CBR, DoR, TTR, PFS, TTP and MRD Negative Rate.
 
Clinical benefit rate (CBR), defined as the percentage of participants with a confirmed minimal response (MR) or better per IMWG
 
Duration of response (DoR) is defined as the time from first documented evidence of PR or better until disease progression (PD) per IMWG, or death due to PD among subjects who achieve an overall response (i.e. confirmed PR or VGPR or

	
CR or sCR). Responders without disease progression will be censored at the censoring time point for TTP.
 
Time to response (TTR) is defined as the time between the date of first dose and the first documented evidence of response (PR or better) for subjects who achieve an overall response (i.e. confirmed PR or VGPR or CR or sCR).
 
Time to best response, defined as the time between the date of first dose and the first best documented response (PR or better) for subjects who achieve an overall response (i.e. confirmed PR or VGPR or CR or sCR).
 
Progression-free survival (PFS) is defined as the time from first dose until the earliest date of disease progression (PD) per IMWG, or death due to any cause. Determination of dates of PFS event and dates for censoring will be described in the RAP.
 
Time to disease progression (TTP) is defined as the time from first dose until the earliest date of PD per IMWG, or death due to PD. Determination of dates of TTP event and dates for censoring will be described in the RAP.
 
For all the TTE endpoints described above, median TTE with 95% CI will be estimated employing the Kaplan-Meier method. A Kaplan-Meier survival curve will be generated. The number and percentage of subjects who had the event or were censored will also be reported. In addition, PFS rate with 95% CI at 6, 12 and 18 months will be estimated using Kaplan-Meier methods for the PFS endpoint.
 
OS is defined as the time from first dose until death due to any cause. Subjects who withdraw consent from the study or are lost to follow-up will be censored at the time of withdrawal or lost to follow-up. Subjects who are still alive at the clinical cut-off date for the analysis will be censored at the last known alive date or last contact date. The last contact date will be determined by the maximum collection/assessment date from among selected data domains within the clinical database. Survival rate 12, 18 and 24 months will be reported from Kaplan-Meier analysis as data permits.

--	---

All subjects who have received study treatment will be evaluated for response according to their originally assigned cohort. The overall response rate (ORR) is defined as the percentage of subjects with confirmed stringent complete response (sCR), complete response (CR), very good partial response (VGPR), and partial response (PR) at any time as per disease specific criteria.

Subjects with unknown or missing response will be treated as non responders, i.e. these subjects will be included in the denominator when calculating the percentage. The number and types of responses, as outlined in International Myeloma Working Group Uniform Response Criteria, will be listed and summarized separately, as appropriate.

The ORR will be reported at futility and at the time of final analyses. The estimates along with 95% exact confidence interval (CI) will be provided.

The clinical Benefit Rate (CBR) is defined as the percentage of subjects with confirmed sCR, CR, VGPR, PR and minimal response (MR) at any time as per disease specific

~~criteria. CBR will be reported at futility and at the time of final analyses. The estimates along with 95% exact confidence interval (CI) will be provided.~~

**Duration of response (DOR)** is defined as time from the first documented evidence of response until the first documented sign of disease progression or death for the subset of subjects who achieve a response (sCR, CR, VGPR, PR). Duration of response will be summarized descriptively, if data warrant, using Kaplan Meier medians and quartiles. Details on rules for censoring will be provided in the RAP.

~~For the analysis of **Progression free survival (PFS)**, PFS Duration is defined from start of the treatment to disease progression or death (due to any cause), whichever comes first. Further details on rules for censoring will be provided in the RAP. PFS will be summarized by dose using Kaplan Meier quantile estimates along with 2-sided 95% CIs at the time of final analysis, if data warrant.~~

~~For the analysis of **overall survival (OS)**, the last date of known contact will be used for those subjects who have not died at the time of analysis; such subjects will be considered censored. Further details on rules for censoring will be provided in the RAP. OS will be summarized by dose using Kaplan Meier quantile estimates along with 2-sided 95% CIs at the time of final analysis, if data warrant.~~

**Reason for change:** Revision of wording for clinical activity endpoints, clarification of ORR and clarification of included population.

## 75. Section 9.7.2.2. – Adverse Events

Adverse events (AEs) will be coded using the standard MedDRA and grouped by system organ class. Adverse events (AEs) will be graded by the investigator according to the National Cancer Institute- Common Toxicity Criteria for Adverse Events (NCI-CTCAE), (version 4.03, [NCI, 2010]). In addition, for GSK2857916 treatment related corneal events, the GSK grading scale for corneal events (Appendix 9) should be used.

Characteristics (e.g. number of occurrences, action taken, grade, etc) of the following AEs of special interest will be summarized separately:

- Corneal events
- Thrombocytopenia
- Infusion related reactions

**Reason for change:** Addition of specific wording related to corneal events and inclusion of AEs which were unintentionally omitted in previous version.

